#### 7.9 Evaluation of Objectives

#### 7.9.1 Primary Safety Endpoint

The primary safety endpoint is freedom from procedure or device-related mortality at 30 days post implant.

#### 7.9.1.1 Hypothesis and/or Parameters to Be Estimated

The objective is descriptive, and no statistical hypothesis test will be performed.

#### 7.9.1.2 Data Collection and Analysis Methods

CEC adjudicated data will be used to assess the safety endpoint. The analysis cohort will be the catheterized cohort. The endpoint will be described by using Kaplan-Meier method. The loglog transformed two-sided 95% confidence interval using the Peto standard error at 30 days will be presented. The primary safety objective will be met if the point estimate of the freedom from procedure or device-related mortality rate at 30 days post-procedure is equal to or greater than the performance target of 95%.

#### 7.9.2 Primary Efficacy Endpoint

The primary efficacy endpoint is percentage of subjects with acceptable hemodynamic function composite at 6 months as defined by:

- Mean RVOT gradient as measured by continuous-wave Doppler ≤40 mmHg
  - o If a catheterization is performed for clinical purposes, the catheterization peak gradient measurement will supersede the continuous-wave Doppler measurement and be used to support the primary endpoint. Acceptable hemodynamic function as measured by catheterization will be considered to be peak gradient ≤40 mmHg.

-AND-

- Pulmonary regurgitant fraction as measured by magnetic resonance imaging <20%

  - If magnetic resonance imaging is contraindicated, a continuous-wave Doppler measurement will be used to support the primary endpoint. Acceptable hemodynamic function as measured by continuous-wave Doppler will be considered to be < moderate pulmonary regurgitation.

-AND-

No prior Harmony valve reinterventions

The primary efficacy endpoint will be calculated using Core lab data, and analysis cohort will be the implanted >24 hours cohort. Analysis method details are provided in section 7.9.2.2.

Revision 5.1

Page 16 of 24

#### 7.9.2.1 Hypothesis and/or Parameters to Be Estimated

The objective is descriptive and no statistical hypothesis test will be performed.

#### 7.9.2.2 Data Collection and Analysis Methods

Core lab data will be used to assess the efficacy endpoint, with an exception in the case that a catheterization is performed to measure mean RVOT gradient, in which site reported data will be utilized. The analysis cohort for the primary efficacy endpoint will be the implanted > 24 hours cohort. The percentage of subjects with acceptable hemodynamic function at 6 month and a two-sided 95% Clopper-Pearson confidence interval will be provided. The primary efficacy objective will be met if the point estimate is equal to or greater than the performance target of 75%.

The efficacy endpoint will be assessed using the 6-month echo, diagnostic catheterization performed during the 6-month protocol window, and reintervention status through 6 months. If 6-month echo occurred prior to 6-month time window opening or missed, next available echo that is after the 6-month window opening will be used, unscheduled or 1-year echo, which ever came first. Tables below define success or failure for all possible scenarios. Only subjects whose procedure were 6 months prior will be included in the analysis. Modified TPV 25 subjects will be excluded from the primary analysis for PMA. The primary endpoint will be evaluated again when all subjects reach 6-month visit.

Previous Reinterventions or Diagnostic Catheterization Procedures			
	6-Month Echo Not Performed or Evaluable	6-Month Echo Acceptable Hemodynamics	6-Month Echo Unacceptable Hemodynamics
Any Harmony Reintervention Prior to 6-Month Window Closing	Fail	Fail	Fail
Diagnostic Cath Acceptable Hemodynamics Prior to 6- Month Window	Not Evaluable	Success	Fail
Diagnostic Cath Acceptable Hemodynamics During 6- Month Window	Success	Success	Success
Diagnostic Cath Unacceptable Hemodynamics Prior to 6- Month Window	Not Evaluable	Success	Fail
Diagnostic Cath Unacceptable Hemodynamics During 6- Month Window	Fail	Fail	Fail

Revision 5.1 Page 17 of 24

No Previous Reinterventions or Diagnostic Catheterization Procedures			
	6-Month Echo Not Performed or Evaluable	6-Month Echo Acceptable Hemodynamics	6-Month Echo Unacceptable Hemodynamics
Previous Echo Acceptable Hemodynamics	Not Evaluable	Success	Fail
Previous Echo Unacceptable Hemodynamics	Not Evaluable	Success	Fail

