## 5. Study Design

This is a prospective, non-randomized, multi-center study. Up to 40 subjects will be implanted at a total up to 15 centers in the United States, Canada, and Japan. It is anticipated that more than 40 subjects will be enrolled (i.e. consented) to meet the target of up to 40 implants as not all subjects will be anatomically suitable for implantation. No site shall implant more than 10 subjects in the pivotal cohort to avoid bias of the study results. Subjects who discontinue participation prematurely following implant will be included in the analysis of results (as appropriate) and will not be replaced in the enrollment of total study subjects implanted. All implanted subjects will receive the Harmony TPV. Each implanted subject will be followed for five years or until the subject's Harmony TPV is explanted.

The addition of the second device size (Harmony TPV 25) is intended to expand the number of patients anatomically suitable for implantation and will include a Roll-In cohort of Harmony TPV 25 subjects. The Roll-In phase is described in **Section 8.4. Harmony TPV 25 Roll-In Phase**. The addition of the larger sized valve completed the pivotal cohort of 40.

Following the completion of the 40 pivotal cohort of the TPV 22 and TPV 25, the TPV 25 was modified and is referred to as modified TPV 25 (mTPV 25). There will be an added cohort of up to 15 subjects implanted with the mTPV 25. This additional cohort will include 10 US implants and up to 5 OUS implants from Canada and/or Japan. The mTPV 25 cohort is described in **Section 8.5. Addition of mTPV 25 Cohort**. The study methods include the following measures to minimize potential sources of bias:

- A Screening Committee comprised of a subset of study investigators will confirm subject eligibility and anatomic suitability
- An external, independent Clinical Events Committee (CEC) will review and adjudicate, at minimum, all deaths and endpoint related adverse events. Safety endpoint results will be based on CEC adjudications.
- All sites will follow a standardized protocol for acquisition of echocardiographic endpoint data.
- An Echo Core Lab will evaluate all echocardiograms.
- A CMR Core Lab will evaluate all functional CMR results.
- Study endpoints, when appropriate, will be based on CEC or Core Lab assessments.
- Study sites will follow their institutional procedures for maintenance of echocardiography and imaging equipment used for assessing the study variables.

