## 8. Study Procedures

### 8.1. Schedule of Events

Evaluation / Visit	Pre-Implant	Implant 	Discharge	1 Month	6 Months	1 Year	Annual (2-5 Years)
Visit Window	Within 24 weeks prior to Implant procedure unless otherwise specified	Implant procedure date	Prior to hospital discharge, or at 30 days post-implant if subject remains hospitalized	Between 2 and 6 weeks after implant	Between 23 and 29 weeks after implant date	Between 44 and 60 weeks after implant date	Between ±8 weeks after the implant anniversary date
Informed Consent	X						
Screening Committee Review	X						
Clinical Assessment	X		X	X	X	X	X
TPV Implant		X					
Echo	X 		X	X	X	X	X
Functional Cardiac Magnetic Resonance Imaging	X 			X 	X		To be completed at 2 & 5 Year Follow-Up
CT Cardiac Angiography	X 		X 				
Fluoroscopy		X		X	X	X	To be completed at 5 Year Follow-Up
Chest X-Ray			X				
SF-36	X 			X	X	X	X
Assessment of Adverse Event/ Device Deficiency	X	X	X	X	X	X	X

 Post-procedure care is carried out according to the standard care of the interventional cardiologist at his/her discretion.

 Clinical Assessment includes: at baseline – subject demographic, medical history, and medication assessment; at follow-up - medication assessment, review of adverse events, and device deficiencies.

 If an echo exam has been performed for routine diagnostic purposes prior to consenting, it can be used as the pre-implant echo exam, provided it was performed within 24 weeks prior to implant. The Principal Investigator must determine if the exam contains the protocol-required data and remains adequate for subject evaluation. If subject is screen failed, functional CMR imaging was used to satisfy the inclusion criteria, and pre-implant echo was not completed within window, a deviation is not required.

 If CMR imaging is contraindicated (e.g., subject has implantable cardiac rhythm device), no deviation will be required for MRI not performed.

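### The SAP's 6-month scoring table lets a site-reported catheter gradient settle the whole efficacy composite, which contradicts the endpoint's separate regurgitation requirement, and no planned analysis tests the dependence on site catheter values

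*SAP*

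**What the plan says.** Protocol Section 5 lists measures to limit bias, among them: "Study endpoints, when appropriate, will be based on CEC or Core Lab assessments". Protocol 12.2.2 and SAP 7.9.2.2 both take the efficacy endpoint from core-lab data, with an exception when "a catheterization is performed to measure mean RVOT gradient, in which site reported data will be utilized".

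The endpoint definition in SAP 7.9.2 has three parts joined by AND:

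- **Gradient.** Mean RVOT gradient by Doppler of at most 40 mmHg. Under this bullet only: "If a catheterization is performed for clinical purposes, the catheterization peak gradient measurement will supersede the continuous-wave Doppler measurement". The catheter criterion follows: "Acceptable hemodynamic function as measured by catheterization will be considered to be peak gradient ≤40 mmHg".
- **Regurgitation.** Regurgitant fraction by MRI below 20%, or less than moderate regurgitation by Doppler if MRI is contraindicated.
- **Reintervention.** No earlier reintervention on the valve.

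SAP 7.9.2.2 limits the catheter rule to "diagnostic catheterization performed during the 6-month protocol window". Protocol 8.1 sets that window as "Between 23 and 29 weeks after implant date". The SAP then states: "Tables below define success or failure for all possible scenarios". The two rows that matter here are:

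| Diagnostic catheterization in window | Echo missing or not evaluable | Echo acceptable | Echo unacceptable |
|---|---|---|---|
| Acceptable | Success | Success | Success |
| Unacceptable | Fail | Fail | Fail |

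SAP 7.9.2.3 plans worst-case, best-case and last-value-carried-forward analyses, all for subjects who could not be assessed. The objective is met if the point estimate reaches 75%. A Clopper-Pearson interval is reported but does not enter the decision.

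**The concern.** There are two linked problems.

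First, the table and the definition disagree. A catheter gradient says nothing about regurgitation under the SAP's own criterion, yet an acceptable gradient gives Success whatever the echo showed. Regurgitation is the condition for which subjects are enrolled (Protocol 7.3), so this is not a marginal component.

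Second, in these rows a site-reported value replaces an independent reading, and no catheterization core lab is named in the protocol synopsis. That may be a sound choice for the gradient, but the plan never shows what the result would be without it. With about 40 subjects and a decision made on the point estimate, one or two reclassified subjects could decide whether the target is met.

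**Working it through.** **Step 1. Apply the definition and the table to the same subjects.** Assume no reintervention.

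| Subject | Definition (SAP 7.9.2) | Table (SAP 7.9.2.2) |
|---|---|---|
| In-window catheter peak gradient ≤40 mmHg; regurgitation component failed | Fail | Success |
| In-window catheter peak gradient ≤40 mmHg; echo missing; regurgitation not known | Not determined | Success |
| In-window catheter peak gradient ≤40 mmHg; Doppler gradient too high; regurgitation component met | Success | Success |
| In-window catheter peak gradient >40 mmHg; echo acceptable | Fail | Fail |

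The conflict is confined to the acceptable-catheterization row. The unacceptable row agrees with the definition, because failing the gradient is enough to fail the composite.

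**Step 2. Check the sensitivity analyses.** A subject with an in-window catheterization gets Success or Fail in every column of the table. Under the table, that subject is never unassessable, so the three analyses in 7.9.2.3 leave the override unchanged. For subjects with no evaluable echo there is a further mismatch: 7.9.2.3 says that the primary outcome excludes them, while the table scores them if they had an in-window catheterization.

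**Step 3. Size of one reclassification.** The documents state no sample-size calculation, power or expected rate, so there is no planned figure to reproduce. Inputs are the 75% target (SAP 7.9.2.2), 40 pivotal subjects and 20 early-feasibility subjects (SAP Section 6). I assume that all are evaluable.

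- Successes needed, r = ceil(0.75 × N): 30 of 40, or 45 of 60.
- Weight of one subject: 100/40 = 2.5 points, or 100/60 = 1.7 points.
- Boundary: 29/40 = 72.5% misses and 30/40 = 75.0% meets; 44/60 = 73.3% misses and 45/60 = 75.0% meets.

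Suppose the planned result sits exactly at target and k net successes came from the catheter rule. The core-lab-only result is (r − k)/N, shown with the 95% Clopper-Pearson interval:

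| k | N = 40 | N = 60 |
|---|---|---|
| 0 | 75.0% (58.8 to 87.3) | 75.0% (62.1 to 85.3) |
| 1 | 72.5% (56.1 to 85.4) | 73.3% (60.3 to 83.9) |
| 2 | 70.0% (53.5 to 83.4) | 71.7% (58.6 to 82.5) |
| 3 | 67.5% (50.9 to 81.4) | 70.0% (56.8 to 81.2) |

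**Step 4. Illustration away from the boundary.** Let X be the number of core-lab successes, binomial with N = 40 and true rate p. The probability of meeting the target with k net gains is P(X ≥ 30 − k). Both p and k are assumptions.

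| Assumed p | k = 0 | k = 1 | k = 2 | k = 3 |
|---|---|---|---|---|
| 65% | 0.121 | 0.205 | 0.314 | 0.441 |
| 70% | 0.309 | 0.441 | 0.577 | 0.703 |
| 75% | 0.584 | 0.715 | 0.821 | 0.897 |
| 80% | 0.839 | 0.912 | 0.957 | 0.981 |

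These figures count net moves from failure to success. Moves the other way would offset them.

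**The case against.** The case for leaving the plan alone has real force.

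- **It is prespecified.** The supersession rule is in the protocol synopsis, Protocol 4.2.2 and 12.2.2, and SAP 7.9.2. The use of site data is an express exception. The safeguard in Protocol Section 5 applies only where appropriate, so a declared exception does not contradict it.
- **It is symmetric.** An unacceptable in-window catheterization turns an acceptable echo into Fail.
- **It is narrow.** Catheterization is not a scheduled follow-up test. One before the window does not override the echo, and any valve reintervention before the window closes is Fail in every column.
- **The definition already confines the catheter to the gradient.** The table also omits MRI in rows with no catheterization, so its wording may be shorthand.
- **'Mean' for 'peak' is editorial**, since the definition says peak throughout.
- **The 29-to-30 example is a boundary case**, and would hold for any reclassification.

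A reader might go further and infer that the rule favours the device, because unblinded sites can turn core-lab failures into successes. The documents do not support that. They describe no masking of site readers, but they also give no frequency of in-window catheterization, and the table moves results both ways.

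Most of this stands, and it limits the point. It does not remove the conflict: the SAP says that the table covers every scenario, so a programmer following it would score a regurgitation failure as Success. Nor does symmetry of the rule mean that moves cancel among 40 subjects.

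**Conclusion.** The concern holds in a limited form. The acceptable-catheterization row contradicts the endpoint definition wherever the regurgitation component is failed or unknown, and this needs correcting whatever the number of subjects affected. The absence of a core-lab-only analysis is a gap in robustness and is not evidence of bias. One net reclassification is worth 2.5 points at n=40 and 1.7 points at n=60, enough to change the conclusion only if the result lies near 75%. The sizes assume full evaluability, and the probabilities also rest on assumed rates and counts. If no subject has an in-window diagnostic catheterization, the numerical effect is zero.

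**What to change.** 1. **Table, SAP 7.9.2.2.** Keep the prespecified catheter rule for the gradient component. State that Success also requires the regurgitation component to be met, by core-lab CMR or by Doppler if MRI is contraindicated.
2. **Data-source sentence, SAP 7.9.2.2 and Protocol 12.2.2.** Say 'peak' for the catheter gradient, to match the definition.
3. **SAP 7.9.2.3.** Add a sensitivity analysis that scores subjects on core-lab echo and CMR only. Treat subjects with a catheterization but no evaluable echo as unable to be assessed. List every subject whose status differs from the primary analysis, in either direction.
4. **Same section.** Reconcile the sentence that excludes subjects without an evaluable 6-month echo with the table cells that score them.

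The cost is one extra analysis and one listing from data already collected, with no new reader, core lab or subjects. The corrected table may give a slightly less favourable rate.

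### SAP 7.9.2.2 scores the primary efficacy endpoint without the MRI regurgitant fraction that SAP 7.9.2 and the protocol require

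*SAP*

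**What the plan says.** **Definition.** SAP 7.9.2 joins three conditions by AND:

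- Doppler mean gradient of at most 40 mmHg. A clinically performed catheterization supersedes this measurement: "Acceptable hemodynamic function as measured by catheterization will be considered to be peak gradient ≤40 mmHg".
- "Pulmonary regurgitant fraction as measured by magnetic resonance imaging <20"%. Doppler regurgitation below moderate is used instead only if MRI is contraindicated.
- No earlier reintervention on the Harmony valve.

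Protocol 4.2.2 and 12.2.2 give the same first two conditions. SAP 7.9.2 then hands over the mechanics: "Analysis method details are provided in section 7.9.2.2".

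**Scoring rule.** SAP 7.9.2.2 states: "The efficacy endpoint will be assessed using the 6-month echo, diagnostic catheterization performed during the 6-month protocol window, and reintervention status through 6 months". It adds: "Tables below define success or failure for all possible scenarios". The two tables cross catheterization, reintervention or earlier-echo status with three 6-month echo columns (not performed or evaluable, acceptable, unacceptable).

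- The row "Any Harmony Reintervention Prior to 6-Month Window Closing" is Fail in all three columns.
- The row "Diagnostic Cath Acceptable Hemodynamics", for a catheterization during the window, is Success in all three columns.

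**Neighbouring sections.** SAP 7.9.2.3 leaves out of the primary calculation any subject without an evaluable 6-month echo. SAP 7.14 declares one change from the protocol, the added reintervention criterion. It says nothing about dropping MRI.

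**The concern.** The section that defines the endpoint and the section that computes it do not describe the same endpoint. A programmer working from 7.9.2 needs the MRI result for every subject without a contraindication. A programmer working from 7.9.2.2 never opens the MRI data. Both would be following the SAP.

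The device is meant to restore valve competence in patients with pulmonary regurgitation (protocol 9.2), so the omitted component is central to the efficacy claim. Catheterization acceptability is a peak gradient with no regurgitation element, yet in the tables it settles the whole composite. The echo label is not defined either: it could mean gradient alone, or gradient plus regurgitation grade.

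Nothing downstream corrects this. The worst-case, best-case and carry-forward analyses in 7.9.2.3 reassign only subjects who could not be assessed, so a Success scored despite a regurgitant fraction of 20% or more stays a Success in all three. Outcome Measure #6 summarises regurgitant fraction separately but does not rescore anyone.

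**Working it through.** **1. Does any cell use MRI?** The tables have 7 rows × 3 columns = 21 cells. None mentions MRI or regurgitant fraction.

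**2. Where do definition and table disagree?** Take subjects with no reintervention and no missing data. Cross in-window catheterization (none, acceptable, unacceptable) with echo gradient (2 levels), echo regurgitation grade (2) and MRI (<20%, ≥20%, contraindicated): 3 × 2 × 2 × 3 = 36 profiles.

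- *Acceptable catheterization, 12 profiles.* The table gives Success in all. The definition gives Fail with MRI ≥20% (4 profiles) and with MRI contraindicated plus echo regurgitation of at least moderate (2). That is 6 false Successes.
- *Unacceptable catheterization, 12 profiles.* Both give Fail.
- *No catheterization, 12 profiles.* The result depends on the undefined echo label.

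| Meaning of acceptable echo | False Success, no cath | False Fail, no cath | Total discordant, including the 6 above |
|---|---|---|---|
| Gradient and regurgitation below moderate | 1 | 1 | 8 |
| Gradient only | 3 | 0 | 9 |

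The single false Fail has an acceptable gradient, echo regurgitation of at least moderate, and MRI <20%. These are counts of profiles, not frequencies of patients.

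**3. What is one subject worth?** The rule is a point estimate of at least 75% (SAP 7.9.2.2). At n = 40, 0.75 × 40 = 30 successes; 30/40 = 75.0% (Clopper-Pearson 95% interval 58.8% to 87.3%) meets it, and 29/40 = 72.5% misses. Each subject is 1/40 = 2.5 points. The denominator is evaluable subjects implanted for more than 24 hours, so 40 is a ceiling. At an assumed 36, the need is 27 and each subject is 1/36 = 2.8 points.

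**4. Illustration with assumed rates.** Chance of meeting the target, from the exact binomial with success probability p + k/n, where k is the expected number of extra successes:

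| n (successes needed) | True rate p | k = 0 | k = 1 | k = 2 |
|---|---|---|---|---|
| 40 (30) | 60% | 0.035 | 0.07 | 0.12 |
| 40 (30) | 70% | 0.31 | 0.44 | 0.58 |
| 40 (30) | 80% | 0.84 | 0.92 | 0.97 |
| 36 (27) | 70% | 0.33 | 0.47 | 0.62 |
| 60 (45), pooled | 70% | 0.24 | 0.34 | 0.45 |

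The 60 is 40 plus the 20 feasibility subjects in SAP 6, again a ceiling. If the echo label includes regurgitation grade, the shift can also be downward: k = −1 at n = 40 and 70% gives 0.20.

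Alternatively, suppose a fraction f of table successes in fact had MRI ≥20%. The rate by definition is then s(1 − f)/40, where s is the number of table successes. For f from 5% to 20% (assumed), 36/40 = 90% falls to between 85.5% and 72%, and 32/40 = 80% falls to between 76% and 64%.

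**5. Evaluability.** SAP 7.9.2.3 excludes subjects without an evaluable echo. In the column "6-Month Echo Not Performed or Evaluable", however, 7.9.2.2 still scores three cells: reintervention (Fail), acceptable in-window catheterization (Success) and unacceptable in-window catheterization (Fail). The choice can move the result either way:

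- Excluding two such Fails turns 29/40 = 72.5% (missed) into 29/38 = 76.3% (met).
- Excluding one such Success turns 30/40 = 75.0% (met) into 29/39 = 74.4% (missed).

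**The case against.** The best defence is that the tables settle only the timing of echo and catheterization, with MRI still in force from 7.9.2. SAP 7.9.2.2 does rely on core-laboratory data, CMR is read by a core laboratory (protocol 5), the section keeps the composite's name, and 7.14 declares no removal of MRI. This reading is possible but weak. The sentence listing the inputs omits MRI, the columns are labelled as echo, and the tables claim completeness. They also score reintervention, a separate component, so they deliver the composite verdict and not just a gradient step. At best the text is ambiguous about the primary endpoint.

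Several narrower points stand:

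- Catheterization is not a scheduled follow-up test. That route needs a clinical catheterization between weeks 23 and 29, so the no-catheterization route may well affect more subjects.
- The documents give no MRI–echo discordance rate and no count of in-window catheterizations. The figures show how sensitive the result is to one subject; they do not measure the actual error.
- SAP 7.9.2.3 can be read as excluding only subjects scored Not Evaluable, but that is not what it says.
- The objective is descriptive, with no hypothesis test. That limits the harm, but the 75% rule still decides whether the objective is met.

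**Conclusion.** The concern holds, and the text must be fixed before the endpoint is computed. SAP 7.9.2.2 contradicts SAP 7.9.2 and the protocol: its scoring rule never uses MRI regurgitant fraction, and without a reintervention an acceptable in-window catheterization is Success whatever the regurgitation. The catheterization route can err only upward. The no-catheterization route errs upward only if the echo label means gradient alone, and in either direction if it includes regurgitation grade.

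The contradiction and the discordant profiles follow from the text without assumptions. The effect on the reported rate is unknown, because the documents do not give the number of affected subjects. Near the threshold a single subject is enough.

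**What to change.** Rewrite SAP 7.9.2.2 to score components under the existing definition:

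- **Gradient:** in-window catheterization peak gradient if done, otherwise core-laboratory Doppler mean with the existing late-echo rule. Catheterization replaces this component only.
- **Regurgitation:** core-laboratory MRI regurgitant fraction below 20%; echo grade below moderate only if MRI is contraindicated.
- **Reintervention:** as now.
- **Combination:** for example, any failed component is Fail, all passed is Success, anything else is Not Evaluable. State that this overrides SAP 7.4, which would drop any subject with missing data. It parallels the missing-element rule for technical and procedural success in SAP 7.11.
- **Echo label:** define it wherever the tables use it.
- **MRI missing, unreadable or out of window without contraindication:** state the rule, for example a missing component. A late-MRI allowance up to the close of the 1-year window would mirror the echo rule, but no 1-year CMR is scheduled, so it would rest on unscheduled scans.

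In 7.9.2.3, exclude subjects scored Not Evaluable under 7.9.2.2, extend the worst-case and best-case analyses to regurgitation, and say what carry-forward uses, since 1-month CMR is required only for mTPV 25 (protocol 8.1). Record the clarification in 7.14. The documents describe the 40-subject pivotal cohort as complete, so if outcomes are already known, report both scorings.

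**Cost:** SAP wording and a small programming change, with no new data for this study. The observed rate may move and a few more subjects may become Not Evaluable. Whether the 20 feasibility subjects have 6-month CMR is not stated; confirm it before pooling, and if it is absent, label the pooled result as using a different regurgitation measure.
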